Military Significance: Traumatic injury to the Central Nervous System (CNS) is an increasing problem for the U.S. military, given the increasing number of soldiers with SCI returning from combat zones. Our proposed project will address this specific need by developing rehabilitative programs and training tools as well as advanced technologies for restoring nerve cell function. Understanding the underlying mechanisms that promote regeneration and recovery, as outlined in this proposal, will contribute to the knowledge base in the field as well as advance current concepts of regeneration. Overall, the aims of this proposal have direct and indirect relevance to military and related civilian populations.

Public Purpose: SCI is a devastating condition that imposes major costs on individuals and society. Close to 12,000 traumatic injuries occur each year in the United States, and approximately 1 million people live with SCI. Moreover, military personnel have returned from combat zones with SCI in the past years. Estimates for lifetime financial burden per individual range from \$500,000 to \$2 million, and costs for SCI patient care in the United States exceed \$7 billion dollars. Including non-traumatic spinal-cord lesions, such as those associated with multiple sclerosis, would quadruple the number and annual cost of U.S. SCI cases [43]. However, virtually all current treatments must be applied shortly after the onset of SCI, as there are not yet effective treatments for the chronic phase of injury [4]. Effective treatment and therapeutic strategies geared toward the chronic injury phase would both improve the lifestyles of people with SCI and decrease their financial burden.

b. Study Design, Research Objectives

Study Design: A 12 months randomized, controlled, single-blinded, in-subject controlled (A-B type) trial will be performed in patients with SCI receiving upper extremity ergometry in combination with FES versus an upper extremities non-FES assisted exercise protocol. Neurological and functional outcome measures will be used at 0, 4, 5, 9, and 12 months to test the efficacy of each intervention.

Specific Aim: Does FES of the upper extremities promote neurological and functional recovery?

Hypothesis 1: Patterned FES of arm and shoulder muscles, via upper extremity ergometry, will improve physical and neurological function in individuals with paralysis resulting from spinal cord injury.

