make a decision to participate in the study. In addition, the candidate will be allowed to discuss the study's appointment logistics with their own care providers. Any questions the potential subject has about the study will be answered. Once the potential subject agrees to participate, the subject will be enrolled and an initial visit will be set up. The subject consent will be obtained during this initial visit before the post-consent screening is performed.

In the 3 years since opening the International Center for Spinal Cord Injury (ICSCI) in 2005 (05'-08'), we have evaluated and treated over 600 new patients with longstanding SCI (White 63.57%, Black 31.69%, American Indian 0.91%, Hispanic 0.36%, Asian 0.18%, Other 3.28%). Currently we evaluate and treat over 250 new patients annually. Of the new patients with long-standing SCI, 50% are ASIA A and B and of this subgroup, over 10% have a neurological level between C1 and C6. Using projections through 08' and bases of 850 system clients, approximately 85 patients will meet the entry criteria of ASIA A-B, neurological level C1-6 proposed in our study. Furthermore, study entry does not have to be limited to clients already within our ICSCI system. Therefore, based on this availability, we do not anticipate the recruitment of patients to be a substantive barrier to recruitment for this study.

b. Target Population:

We plan to enroll up to 30 subjects with an expected accrued number of subjects of 24 (screening failure of 6). The 24 accrued subjects will be randomized in 2 groups of 12. We are anticipating an attrition rate of 4 subjects maximum.

We plan to enroll both male and female subjects, all ethnic groups.

No specific racial or ethnic groups will be targeted by our recruitment process.

Non-English speaking subjects will not be targeted by our recruitment process.

No vulnerable population is specifically targeted by our recruitment process.

Pregnant women will be excluded from this study.

c. Recruitment Material:

Subject Recruitment Flyer: form given to ICSCI patients that fit the study criteria during a clinic visit, and posted on the ICSCI website (www.spinalcordrecovery.org).

Inclusion/Exclusion Index Card: Laminated index cards with inclusion/exclusion criteria that physician can carry.

Inclusion/Exclusion Wall Listing: Laminated listing with inclusion/exclusion criteria posted in ICSCI clinic rooms that physician can refer to.

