h) Action Research Arm (ARA) test: This is a routine exam performed for people with spinal cord injury. The ARA test observationally assesses upper extremity function (20 items, ordinal scale [57]). Subjects are tested in a seated position, preferably from their wheelchairs, in front of a table. Test items will be laid out on the table and the test conducted per the standardized instructions. The ARA requires subjects to handle objects differing in size, weight and shape.

i) Functional Reach (FR) test: This is a routine exam performed for people with spinal cord injury to evaluate trunk balance. The test is performed by patient reaching forward as far as they can while seated in their wheelchair. The distance traveled by the top of the reference shoulder is measured. 2 practice trials and 1 actual reach test is performed for the purpose of the study.

j) Range Of Motion (ROM) of the upper extremity joints: This is a routine exam performed for people with spinal cord injury. The Range Of Motion of the shoulder, elbow, wrist, and metacarpal-phalangeal joints will be measured via goniometry. Subjects are tested in a seated position, preferably in their wheelchairs. The desired joint is isolated and moved through the maximum available range of motion. Once the end range is reached, joint excursion is measured with a goniometer.

k) Numerical Rating Scale (NRS) for pain: This is a routine exam performed for people with spinal cord injury. Subjects report how much pain they are having by choosing a number from 0 (no pain) to 10 (the worst pain imaginable) (ordinal scale, [48]).

l) Pulmonary Function Test (PFTs): This is a routine exam performed for people with spinal cord injury. Three respiratory functions will be measured. Vital Capacity (VC) is the maximal amount of air that can be exhaled after a maximal inhalation. Negative Inspiratory Force (NIF) is the ability to take a deep breath in and to generate a cough strong enough to clear secretions. Peak Cough Flow (PCF) measures the expiratory muscle force and the ability to cough.

m) American Spinal Injury Association (ASIA) exam: This is a routine exam performed for people with spinal cord injury. The ASIA exam assesses motor function at 10 key muscles in the body and light touch and pinprick sensation at 28 key points on each side of the body. It is also used to classify injury level and severity (ordinal scale, [49]).

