* PI: Principal Investigator, CoI1: Co-Investigator 1, CoI3: Co-Investigator 3, T1-7: Therapist 1-7, N1: Nurse 1, N2: Nurse 2, N3: Nurse 3, SC2: Study Coordinator2.

Table 1: Data Collection Schedule

(2) Intervention:

There are a total of 96 visits: 48 FES assisted intervention visits scheduled 1 hour, 3 times a week for 4 months, and 48 non-FES assisted exercise regimen visits scheduled 1 hour, 3 times a week for 4 months.

3. Blinding, including justification for blinding or not blinding the trial, if applicable.

The evaluator will be blinded to group assignment for the following assessment, but we cannot use true blinding due to the intervention's sensory component:

- c. Severity of gleno-humeral subluxation
- d. Spasticity measurement
- e. Capabilities of the Upper Extremity test
- f. Jebsen-Taylor Hand Function test
- g. Box and Blocks test
- h. Action Research Arm test
- i. Functional Reach test
- j. Range Of Motion of the upper extremity joints
- m. American Spinal Injury Association (ASIA) exam

4. Justification of why participants will not receive routine care or will have current therapy stopped.

All subjects will continue to consistently perform their usual (“baseline”) amount of physical activity throughout the study, including performance of lower extremities assisted FES ergometry, home exercise stretching program, cardiovascular conditioning, etc. “Baseline” activity is defined as amount of physical activity performed for at least 1 month prior to enrollment. Routine care will not be interrupted.

5. Justification for inclusion of a placebo or non-treatment group.

Both groups will receive some type of intervention: upper extremity passive ergometry or FES assisted upper extremity ergometry. This way, the effect of FES application will be extracted.

6. Definition of treatment failure or participant removal criteria.

Treatment failure constitutes of:

- Increased pain (more than 3 points increase on the NRS).
- Increased shoulder subluxation (more than 1 cm).
- Decreased range of motion (more than 15 deg).

Subjects will be removed from the study if they:

- Requires significant hospitalization (that would interfere with physiologic processes proposed to be studied through the protocol, i.e. e-stim) – at the discretion of PI.
- Become pregnant.

7. Description of what happens to participants receiving therapy when study ends or if a participant's participation in the study ends prematurely.

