Power analysis: Because upper extremity, FES-assisted ergometry training is a new intervention, we based our power analysis on previously completed studies that looked at the effect of FES on muscle mass (50, 51) and cardio-vascular conditioning (52-56). A sample size of 24 will allow us to detect a mean difference between the pre- and post-measures. Some of our outcome measures (CUE, JTHF, BB tests) have been shown to respond to many types of rehabilitative interventions, and we believe they will be particularly responsive to the type of training used here. One of our goals is to use the data obtained in this study to determine the magnitude of the effect so we can design future trials. If the magnitude is very small, however, it is unlikely to be clinically relevant. We would then be more likely to propose intensifying the intervention (e.g., by lengthening the periods of cycling) than to suggest increasing sample size.

4. Early stopping rules.

* Subject medical status:

- Requires significant hospitalization (that would interfere with physiologic processes proposed to be studied through the protocol, i.e. e-stim) – at the discretion of PI.
- Increased pain (more than 3 points increase on the NRS).
- Increased shoulder subluxation (more than 1 cm).
- Decreased range of motion (more than 15 deg).

* Subject not compliant:

- Fails to follow directions.
- Become pregnant.

XII. LABELING & STORAGE OF DATA & SPECIMENS

All paper study documents are stored in locked cabinets at the Broadwaycampus of the KKI-ICSCI. Access to the locked cabinets is strictly limited to the study team members listed on this protocol. The documents with identifiers (such as the consent forms, phone screening forms, and the document that links the subject study # to the identity of the subject) are stored in a study binder in a separate locked cabinet from hard copy data collection forms.

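### Sections XI.a.6 and XI.c.4 leave open whether crossing the pain, subluxation or ROM threshold ends training or participation; ending participation would lose later data because of the subject's own outcome

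*Combined protocol and SAP*

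**What the plan says.** Section XI.a.6 has two lists. The first opens with "Treatment failure constitutes of" and names three events: "Increased pain (more than 3 points increase on the NRS", "Increased shoulder subluxation (more than 1 cm" and "Decreased range of motion (more than 15 deg". The second opens with "Subjects will be removed from the study if they" and names only significant hospitalization and pregnancy.

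Section XI.c.4 (Early stopping rules) repeats the three thresholds unchanged. They share a sub-list on medical status with hospitalization. Pregnancy is in a second sub-list, on non-compliance. No sentence says what stops, and neither section names the visit against which a change is measured.

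Section XI.a.7 covers a subject whose participation ends early, but only by offering FES ergometry outside the study.

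Section XI.c.1 lists subluxation, range of motion (ROM) and pain among the dependent variables. Section VII.b describes the design: "A 12 months randomized, controlled, single-blinded, in-subject controlled (A-B type) trial will be performed in patients with SCI". On losses, section IX.b says: "We are anticipating an attrition rate of 4 subjects maximum".

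**The concern.** The two sections point different ways. XI.a.6 makes the three events a status that is separate from leaving the study. XI.c.4 groups them with events that XI.a.6 treats as grounds for leaving. Two staff members could each follow the protocol and handle the same subject differently: one stops training and keeps the assessments, the other ends participation.

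The triggers are themselves outcomes. If participation ends, later data go missing because the subject got worse on a dependent variable. That loss depends on the outcome, and the analysis plan in XI.c.3 does not say how such subjects are handled. Each subject is meant to receive both regimens, so a subject lost after the first block has no FES versus non-FES comparison of their own. The trial is small, so each such loss counts. Table 1 also shows pain rated by an unblinded assessor, so uneven use of an unclear rule could differ between the sequences.

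**Working it through.** **1. The two sections side by side**

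| Event | XI.a.6 failure list | XI.a.6 removal list | XI.c.4 stopping list |
|---|---|---|---|
| Pain up more than 3 NRS points | yes | no | yes |
| Subluxation up more than 1 cm | yes | no | yes |
| ROM down more than 15 degrees | yes | no | yes |
| Significant hospitalization | no | yes | yes |
| Pregnancy | no | yes | yes |

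All three thresholds appear in both sections with the same values. None is in the removal list. XI.c.4 does not separate them from the two removal grounds.

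**2. When a scheduled reading can trigger the rule, and what removal would cost**

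Table 1 schedules pain and ROM at months 0, 4, 5, 9 and 12, and the shoulder X-ray at 0, 4, 9 and 12. The blocks run from month 0 to 4 and from month 5 to 9.

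| Crossing found at | Events that can trigger | Second block at stake? | Assessments lost if removed |
|---|---|---|---|
| Month 4 | all three | yes | months 5, 9, 12 |
| Month 5 | pain and ROM only (no X-ray) | yes | months 9, 12 |
| Month 9 | all three | no, already given | month 12 |

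The reading that triggers the rule has already been taken, so it is not lost. A first-period comparison of the two groups at month 4 survives a crossing found at that visit.

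**3. Precision of a paired comparison**

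The plan gives no effect size, SD, power or sidedness, so its sample size of 24 cannot be reproduced. The relative loss needs none of these. If *m* of 24 subjects have no second block, the standard error of the mean within-subject difference grows by √(24/(24 − *m*)):

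- *m* = 1: √(24/23) = 1.022, a rise of 2%.
- *m* = 4, the ceiling in IX.b: √(24/20) = 1.095, a rise of about 10%.

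For scale only, assume 80% power at two-sided 0.05 in a two-period crossover (noncentral t, *n* − 2 degrees of freedom). The detectable difference, in SDs of the within-subject difference, moves from 0.60 with 24 completers to 0.66 with 20. At the effect detectable with 24, power falls from 80% to 72% with 20.

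**4. Bias**

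This cannot be computed. It depends on how many subjects cross, in which regimen, and how they would have fared later. The documents give none of these.

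**The case against.** **The sections can be reconciled.** Failure is a status, early stopping means stopping training, and removal is separate. This is a sensible reading, and it is the one the fix writes down. The text does not state it, and XI.c.4 mixes the three events with removal grounds.

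**Some consequence is stated.** A reader might infer that the plan attaches none at all to crossing a threshold. That goes too far: the heading of XI.c.4 says that something stops. Only the scope is open. XI.a.7 does not settle it, because it says nothing on the second block or on later assessments.

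**The plan does not commit to a paired analysis.** XI.c.3 mentions comparisons between groups as well as repeated measures, and the month-4 value is kept. This stands. The figure of about 10% applies to a paired comparison and not to every analysis.

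**A larger loss.** A reader might add stopped subjects to the 4 anticipated losses; 4 more would give √(24/16) = 1.22. IX.b gives 4 as the maximum and does not exempt stopped subjects, so this may count the same people twice.

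**False ROM triggers.** A reader might infer that goniometer error alone would stop many subjects, and ask for a confirming reading. XI.a.1 says only "Once the end range is reached, joint excursion is measured with a goniometer". The documents give neither the measurement error nor the number of readings, and the ROM form is not reproduced. With assumed standard errors of measurement of 3 to 5 degrees and 8 to 20 independent readings, the rate over months 4 and 5 runs from 0.3% to 47%. That range supports no conclusion, and a required repeat would make a safety rule less sensitive.

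**Timing.** Pain can also be reported during supervised sessions, so months 4 and 5 are the scheduled decision points but not the only possible ones.

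**Conclusion.** The point holds as an unresolved conflict over scope. XI.a.6 keeps the three events apart from removal, XI.c.4 lists them with removal grounds, and nothing in the plan says that assessments continue after a stop. If XI.c.4 is read as ending participation, later data are lost because of the subject's own result on a dependent variable.

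The number who would cross is unknown. Within the stated ceiling of 4 losses, the standard error of a paired comparison rises by at most about 10%, assuming that stopped subjects count toward that ceiling and that each lacks a second block. The bias may matter more than the lost precision, but it cannot be sized. This is worth correcting because the correction is cheap. It does not invalidate the design.

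**What to change.** Put the same text in XI.a.6 and XI.c.4:

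- A rise in pain of more than 3 NRS points, a rise in subluxation of more than 1 cm, or a ROM loss of more than 15 degrees, each relative to the initial visit, is a treatment failure.
- It may stop further training, including the second block, if the investigator judges this necessary for safety and records the decision.
- It does not remove the subject from the study. The subject attends all remaining scheduled assessments.
- All readings, including the one that triggered the rule, stay in the analysis.

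Leave hospitalization and pregnancy as removal grounds. If anyone has already been stopped on one of the three events, report the event, the visit and what was stopped.

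The change does not guarantee a second block. It protects the follow-up data and the comparison of the groups as randomized, but not every within-subject comparison.

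The cost is a wording amendment, which may need prior approval under XVIII.a if it is seen as loosening a safety rule, plus the remaining visits for stopped subjects. By the visit lengths in Table 1, a subject stopped at month 4 would still attend 3 2/3 + 4 1/4 + 4 1/4 = about 12 hours of assessments, all already scheduled. No visit or X-ray is added.

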q) Non-FES Upper Extremity Exercise: While undergoing the non-FES exercise intervention, the subjects will receive a specific, individualized exercise regimen, consisting of strengthening, stretching, splinting and any other therapeutic interventions that do not use electrical stimulation.. The subjects will remain seated in their primary wheelchair throughout the treatment. The subjects will exercise for 60 minutes/session, three times a week for 4 months.

2. Study duration and number of study visits required of research participants.

The study will last 12 months. The Study Time Line is found in Figure 1, and the Data Collection Schedule in Table 1.

(1) Assessment:

The following post-consent screening will be performed at the Initial visit:

- a. Neurological Exam (about 30 minutes)
- b. Fast Urine Pregnancy Test (about 15 minutes)

The following assessments will be performed at the Initial Visit:

- o. FES Evaluation (about 15 minutes)

The following assessments will be performed at the Initial, 4th month, 9th month, and 12th month Visits:

- c. Severity of gleno-humeral subluxation (about 30 minutes)

The following assessments will be performed at the Initial, 4th month, 5th month, 9th month, and 12th month Visits:

- d. Spasticity measurement (about 15 minutes)
- e. Capabilities of the Upper Extremity test (about 10 minutes)
- f. Jebsen-Taylor Hand Function test (about 15 minutes)
- g. Box and Blocks test (about 15 minutes)
- h. Action Research Arm test (about 20 minutes)
- i. Functional Reach test (about 5 minutes)
- j. Range Of Motion of the upper extremity joints (about 30 minutes)
- k. Numerical Rating Scale (NRS) for pain (about 1 minutes)
- l. Pulmonary Function Test (PFTs) (about 5 minutes)
- m. American Spinal Injury Association (ASIA) exam (about 60 minutes)
- n. Pain and Spasticity Medication inventory (about 10 minutes)

	Initial	4 th Month	5 th Month	9 th Month	12 th Month	Test Evaluator*	Blinded
	5 hours	4 1/2 hours	3 2/3 hours	4 1/4 hours	4 1/4 hours		
Neurological Exam	√					PI, CoI1	No
Fast Urine Pregnancy	√					N1, N2, N3	No
Shoulder X-Ray	√	√		√	√	PI, CoI3	Yes
Modified Ashworth	√	√	√	√	√	PI, CoI1	Yes
CUE	√	√	√	√	√	T1,T6	Yes
JTHF	√	√	√	√	√	T1,T6	Yes
BB	√	√	√	√	√	T1,T6	Yes
ARA	√	√	√	√	√	T1,T6	Yes
FR	√	√	√	√	√	T1,T6	Yes
ROM	√	√	√	√	√	T1,T6	Yes
Pain NRS	√	√	√	√	√	PI, CoI1, SC2	No
PFTs	√	√	√	√	√	N1, N2, N3	No
ASIA	√	√	√	√	√	PI, CoI1	Yes
Meds Inventory	√	√	√	√	√	PI, CoI1, N1, N2, N3, SC2	No
FES Eval	√					T1,T6	No

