We will be offering FES assisted upper extremity ergometry through our Open Gym program or, if rehabilitative care requires it, though an ongoing, patient tailored program.

b. Devices

1. Name of Test Device:

RT300-SLSA

Manufactured by: Restorative Therapies, Inc
[name]
[name]
[contact]
[contact]

2. Schedule/duration/administration of test device:

The RT300-SLSA Cycle Ergometer is the only device capable of upper extremity cycle ergometry with and without FES, for use in the study.

The device will be used for 1 hour, three times a week, for 4 month,, by both the FES and Control group. For the Treatment group, the device will be programmed to deliver synchronized electrical pulses to the upper extremities. For the Control group, the device will be programmed to drive the cycling of the upper extremities.

Device Risk Assessment: The RT300-SLSA cycle ergometer is a motorized system that allow for purely passive, active, or assisted control over leg or arm cycling. The stimulation system is fully integrated with leg and arm motors (“dynamic motor support”) with unilateral or bilateral stimulation option, allowing for individualized usage for upper and lower extremities. The systems allow for the individual to remain in his/her wheelchair, insuring easy usage across subjects without transfer of the subjects. The speed of cycling can be changed from zero to sixty revolutions per minute (rev/min) and the load (resistance) can be adjusted from zero to 17 Newton-meters (Nm). The system has numerous safety features, such as muscle spasm detection and arm guides, that make it ideal for use in this study. The system have internet connectivity allowing the retrieval of subject settings and the automatic collection of cycling data, ensuring easy use across subjects in this study.

All the ergometers that will be used for this study will be checked and tagged by Johns Hopkins Hospital Clinical Engineering Services (CES). The local IRB of Record does require an approval letter from CES regarding the use of the device in the study. The approval letter is part of the application to the local IRB of Record.

3. FDA Status:

The device is classified as an external functional neuromuscular stimulator (CFR 882.5810). The device is FDA cleared under section 510(k). The device clearance number is K072398.

The device will be used in a research mode that:

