- 1] allows the stimulation of our proposed list of upper extremity muscles (supraspinatus; infraspinatus; teres major and minor; anterior, middle, or posterior deltoid; biceps; and triceps), which is more than the standard set of muscles (bilateral biceps, triceps and supraspinatus).
- 2] allows to change the timing of the stimulation (On/Off) to produce a smooth cycling motion.

4. FDA approved use description:

The device FDA indication for use are:

1. Relaxation of muscle spasms
2. Prevention or retardation of disuse atrophy
3. Increasing local blood circulation
4. Maintaining or increasing range of motion

5. IDE Info:

Not applicable

c. Study Statistics

1. Primary outcome variable.

Independent Variables

FES or no FES

Dependent Variables: to be measured at 0, 4, 5, 9 and 12months

Severity of gleno-humeral subluxation, measured by X-ray (not measured at 5 months).

Spasticity of the pectoralis, biceps, triceps, and long finger flexor muscles, measured with the Modified Ashworth.

Functional movement of the shoulder, measured with the Capabilities of the Upper Extremity (CUE) test.

Hand function, measured with the Jebsen-Taylor Hand Function (JTHF) and Box and Blocks (BB) tests.

Upper limb function measured with the Action Research Arm test (ARA) test.

Range Of Motion of the upper extremity joints (of the shoulder, elbow, wrist, and fingers/thumbs), measured with goniometry.

Pain, measured with the Numerical Rating Scale (NRS).

Neurological function, measured with the American Spinal Injury Association (ASIA) exam.

2. Secondary outcome variables.

Not applicable

3. Statistical plan including sample size justification and interim data analysis.

Data Analysis: Data will be collected in accordance with each instrument's standardized instructions, with the evaluator being blinded to group assignment. To obtain consistency and facilitate interpretation of the data, we will use means and standard deviations (SDs) to describe normally as well as non-normally distributed variables. Appropriate post-hoc statistical analysis will be used to compare between group means and repeated measures. Baseline tests of homogeneity will be used *a priori*. If statistically significant differences are found after the subjects are randomized to the two groups, they will be corrected in the post-hoc analysis. Results will be considered significant at $P<0.05$.

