Accurate and complete study records will be maintained and made available to representatives of the U.S. Army Medical Research and Materiel Command. These representatives are authorized to review research records as part of their responsibility to protect human research volunteers. Research records will be stored in a confidential manner so as to protect the confidentiality of subject information.

XIII. RISK AND INJURY

a. Risks, Risk Management:

All assessments and intervention sessions will be supervised by the Principal Investigator.

For all the study procedures, the risks and risk management are defined in the sections below.

1. Assessment Risks:

a) Neurological Exam: During testing, the subject might experience pain induced by hitting/tapping of the arm, but usually, the sensation experienced is a quick, non-painful touching sensation. To minimize the risk, one of the study team member trained in the procedure will perform the test.

b) Fast Urine Pregnancy Test: There is the possibility of psychological stress occurring if testing shows that the subject may be pregnant. To minimize the risk in the event that pregnancy test results are positive, the result will be disclosed to the subject. If the subject is uncomfortable with this arrangement, his/her consent to participate in this study is not recommended.

c) Severity of gleno-humeral subluxation: The subjects receive ionizing radiation due to the diagnostic bilateral shoulder X-ray procedures they receive at the Initial, 4th Month, 9th Month, and 12th Month visit. The Total Effective Dose from the procedures is 0.4 rem. This is more than the 0.3 rem that the average person in the United States gets each year from natural sources like the sun, outer space, air, food and soil. It is less than the 5 rems of radiation that is allowed each year for people who are exposed to radiation in their jobs. To minimize the risk, pregnant women are excluded from the study.

d) Spasticity Measurement: There is a risk of eliciting spasms during the test. Subjects will feel a quick pull of the muscle, which might be painful at times. To minimize the risk, one of the study team member trained in the procedure will perform the test.

e) Capabilities of the Upper Extremity (CUE) test: There are no known risks associated with this test.

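### Hospitalization takes a randomised subject out of the study rather than only off the intervention, and the criterion is worded around the stimulation that only one of the two blocks delivers

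*Combined protocol and SAP*

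**What the plan says.** XI.a.6 introduces its removal list with "Subjects will be removed from the study if they", and the first item is "Requires significant hospitalization (that would interfere with physiologic processes proposed to be studied through the protocol, i.e. e-stim", left to the PI's discretion. XI.c.4 (Early stopping rules) repeats that item. It adds a rise in pain of more than 3 points, an increase in subluxation of more than 1 cm and a loss of range of motion of more than 15 degrees. XI.a.6 calls those three treatment failure and does not list them as grounds for removal. All three are also dependent variables in XI.c.1.

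Every subject is scheduled for both 4-month blocks, in randomised order, 12 per order (XI.a.1). The comparison block is strengthening, stretching, splinting and other "therapeutic interventions that do not use electrical stimulation". XI.a.5 and XI.b.2 describe it instead as passive ergometry, also without stimulation.

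On early exit, XI.a.7 says "We will be offering FES assisted upper extremity ergometry through our Open Gym program", or a tailored program where care requires it. It does not mention assessments. XI.c.3 says "Appropriate post-hoc statistical analysis will be used to compare between group means and repeated measures" and names neither an analysis set nor a method for subjects who leave. IX.b says "We are anticipating an attrition rate of 4 subjects maximum", without splitting the losses by cause or order.

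**The concern.** Two things are combined in one rule. First, the consequence is removal from the study, so a subject who has a serious setback after randomisation stops contributing outcomes. Stopping the intervention may be necessary; stopping measurement is not. With 24 subjects, each lost pair matters, and the subjects lost are those whose course was disturbed.

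Second, the criterion is tied to e-stim, which is the exposure under comparison. If it is applied literally, a stay during FES can take the subject out before that block's outcome is measured, while the same stay during exercise leaves a poor exercise score in the data. That would favour FES.

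**Working it through.** **The plan's own figure.** XI.c.3 gives N = 24 with no effect size, SD or power, so it cannot be reproduced. As a yardstick, an assumed paired t-test (two-sided 0.05, 80% power) detects 0.597 SD of the paired difference with 24 pairs and 0.660 SD with 20.

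**Three readings of the criterion** (blocks at months 0–4 and 5–9, follow-up to month 12):

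- Block reading: only stays while FES is being delivered count. Exposure is 4 months in each order. An FES-first subject then misses 4 of 5 assessments (months 4, 5, 9, 12) and an exercise-first subject misses 2 of 5 (months 9, 12).
- Order reading: stays count while e-stim is current or still to come. Exposure is months 0–4 for FES-first and 0–9 for exercise-first. At an assumed annual risk of 10%, 20% or 30% (constant rate), expected removals per 12 are 0.41 against 0.91, 0.86 against 1.85, and 1.35 against 2.82.
- Neutral reading: any significant stay during the programme counts, whatever the block.

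**Illustrative bias.** Assumptions, none of them in the documents: a stay has probability p over the year and is equally likely in every month; it lowers the score by d at the end of the block in which it falls; the drop does not carry into the next block; there is no true effect; completers are analysed.

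- Block reading: removals k = 24(p/3). Among those remaining, the share with a stay in the exercise block is (p/3)/(1 − p/3), so bias = d·k/(24 − k).
- Order reading: k = 12(p/3) + 12(0.75p) = 13p. Only the FES-first group keeps exercise-block stays, so bias = ½·d·(p/3)/(1 − p/3).

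| k removed | Block reading: p, bias | Order reading: p, bias | Neutral |
|---|---|---|---|
| 1 | 0.125, 0.043 d | 0.077, 0.013 d | 0 |
| 2 | 0.25, 0.091 d | 0.154, 0.027 d | 0 |
| 4 | 0.50, 0.200 d | 0.308, 0.057 d | 0 |

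k = 4 is a ceiling: it uses up the plan's whole allowance for losses, and under the block reading it needs half of all subjects to be hospitalized within the year.

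**Does a repeated-measures model remove it?** Simulation at p = 1/6, d = 1 SD, assumed within-subject correlation 0.5, generalised least squares on all available data (simulation SE 0.002): block reading 0.059, order reading 0.032, removal in both blocks −0.002, all assessments kept 0.000. Completers give 1/17 = 0.059 and half of that, 0.029. So it does not in this one scenario, which shares the no-carryover assumption.

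**Sensitivity to carryover.** Suppose the drop persists and score levels are compared. An exercise-first subject hospitalized during exercise then carries it into both scores and it cancels. The block-reading bias halves (k = 2: 0.091/2 ≈ 0.045 d). The order-reading bias rises by a quarter, because washout stays in the FES-first group now count: (p/3 + p/12)/(p/3) = 1.25. If subjects recover before the block-end visit, both go toward zero.

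**Would keeping the assessments be enough alone?** Let each block give benefit g in proportion to sessions delivered, and apply the order reading.

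- FES-first: stops in months 0–4 cost FES (p/3)(½) = p/6 and exercise p/3, net +p/6.
- Exercise-first: stops in block 1, washout and block 2 give −p/6 − p/12 − p/6 = −5p/12.
- Average: (p/6 − 5p/12)/2 = −p/8, or about −0.02 g at p = 1/6.

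If the criterion covers either intervention, the two orders give +5p/12 and −5p/12, which cancel. Both changes are therefore needed.

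**The case against.** The strongest reply is that the block-specific reading has to be supplied by the reader. The main clause refers to the processes the protocol studies, not to what is being delivered that month. Every subject is due to receive both interventions, and *i.e. e-stim* may be loose shorthand for the programme as a whole. Usual lower-limb FES may also continue throughout (XI.a.4), so e-stim in the wide sense is not confined to one block. This stands: the documents support a neutral reading, and PI discretion could apply the rule evenly. What remains is that the text does not require that reading.

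It can also be said that the end of data collection is inferred. That is fair. It is the ordinary meaning of removal from the study, and XI.a.7 answers a question about therapy, so its silence on assessments is weak evidence. Still, no text anywhere provides for them.

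A third reply is that the pain, subluxation and range-of-motion stops are tied more directly to outcome than hospitalization is, since they are dependent variables. This is correct, and the fix covers them.

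A reader might infer that removals are decided by someone who knows the block, because XIII.a says "All assessments and intervention sessions will be supervised by the Principal Investigator". But XI.a.3 says "The evaluator will be blinded to group assignment for the following assessment", and Table 1 lists the PI among the blinded evaluators for X-ray, Ashworth and ASIA. The documents do not settle this, and nothing above depends on it.

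**Conclusion.** The point holds as a minor one, a cheap improvement. On its ordinary meaning, the rule ends outcome collection for randomised subjects after a significant hospitalization, which loses data selectively in a 24-subject crossover. Its wording also leaves room for losses that differ by block or order.

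A reader might go further and conclude that the rule does bias the trial toward FES. The documents do not support that. One supported reading gives no bias from differential removal, and the other two tilt toward FES only under the assumptions listed. No hospitalization rate or score drop is given, so the size cannot be computed. The illustrative values, 0 to 0.09 d for two removals, depend on the drop being present at the block-end visit and not carrying over. They are not estimates. For d = 1 SD of the paired difference they are well below the 0.60 SD detectable with 24 pairs.

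Nor would keeping the assessments remove the problem completely: it depends on the subject's agreement, and without the wording change it can leave unequal intervention stops by order.

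**What to change.** Make both changes together, in XI.a.6 and XI.c.4.

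1. Replace *i.e. e-stim* with *i.e. either study intervention*, applied identically in both blocks and both sequences.
2. State that meeting this criterion, or the pain, subluxation or range-of-motion criteria in XI.c.4, stops the study intervention only. The remaining scheduled assessments continue if the subject agrees, all collected data are analysed in the randomised sequence, and any later Open Gym FES is recorded.

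Cost: two short edits and no new procedures. A subject stopped in the first block has at most 4 remaining visits, 4.5 + 3.67 + 4.25 + 4.25 = 16.67 hours and 25 + 25 + 25 + 50 = $125. For four such subjects that is 16 visits, about 67 hours and $500. At an assumed stay probability of 1/6, hospitalization alone adds about 1.33 × 4 + 0.33 × 3 + 1.33 × 2 = 9 visits.

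Downsides, at the same 1/6: compared with the block reading, expected in-block stops rise from 24/18 = 1.3 to 48/18 = 2.7 of 24, plus 0.3 if washout stays count. Keeping stopped subjects in their sequence dilutes a true FES effect by (p/3)(0.75 + 0.25) + (p/12)(0.5) = 0.0625, about 6%, if benefit is proportional to sessions delivered. Stops for pain, subluxation or range of motion would add to both the visits and the dilution.
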